Our study team will use social media to reach potentially eligible participants. We have developed a Facebook page for posting IRB-approved study flyers and information for this and other studies in the Traumatic Stress and Health Research Laboratory, <https://www.facebook.com/Duke-Traumatic-Stress-and-Health-Research-Lab-379366159145563/>. We plan to place pictures of our study flyers on the Facebook page, and use Facebook's post boost to draw attention to the post. The post itself will say "Enroll now!" or "Now enrolling!" We will also plan to use Facebook ads to target potential participants within a 50-mile radius of Duke. If any participant contacts the email associated with the Facebook page ([contact]), he/she will be sent an automatic email response.

Based on our previous studies, we expect to screen 250 participants to enroll and randomize 140. Eligibility criteria for the current trial include:

- are an enrolled veteran at the DVAHCS for primary care,
- can read/write/speak fluent conversational English,
- have current AUD (meeting past month DSM-5 criteria), and
- are willing to make a quit attempt and/or reduce alcohol use to low risk levels.

Exclusion criteria are:

- have fewer than 3 days of abstinence,
- have a history of clinically significant alcohol withdrawal, as indicated by 1) a score of 10 or more on the Clinical Institute Withdrawal Assessment of Alcohol (CIWA), 2) past medical alcohol detoxification, or 3) a history of seizures or hallucinations during alcohol withdrawal.
- is current imprisoned or hospitalized on an inpatient psychiatric unit,
- have had a seizure as an adult (e.g., child febrile seizures not exclusionary),
- is unwilling to sign a VA consent form to retrieve medical records, or
- is currently receiving professional behavioral treatment for AUD.

Veterans with a history of clinically significant withdrawal will not be eligible to participate, and will be referred to their providers for evaluation of medical management of clinical detoxification.

D.3. Study Screening Session and Randomization

[figure not shown]

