Potential participants who discuss the study with study personnel will complete a brief phone screen to assess potential eligibility. Veterans who are potentially eligible will attend a screening session where they will complete diagnostic interviews, self-report measures, urine drug screen and alcohol breathalyzer to determine inclusion. Participants who screen in will be randomized at the first treatment session to one of two treatment conditions (CBT+mCM vs. CBT alone) and to one of two long term incentive conditions (abstinence incentive at 6 months vs. No incentive). Stratified permuted block randomization assignments will be performed using a computerized sequence generated by the study statistician before the study starts. The sequence will be password-protected so that only the statistician and other study staff who do not have patient contact will have access to the sequence. We will stratify on the presence of comorbid non-tobacco SUD.

D.4. Interventions

D.4.1. Cognitive-Behavioral Therapy for Substance Use Disorders

We will use the VA CBT for SUD protocol (DeMarce, Gnys, Raffa, & Karlin, 2014) to provide in-person treatment in both study arms. CBT will be provided by a therapist with at least a Master's degree in mental health (e.g., psychology, social work) who has reviewed CBT for SUD training materials. To prevent confounding from therapist effects, study therapists will treat cases in both study arms. CBT sessions will be weekly over 12 weeks as shown in Figure 3. Following the standard of care for AUDs, all participants will be referred to aftercare and encouraged to participate in 12-step programs following completion of the 12-session CBT intervention (Proctor & Herschman, 2014).

Figure 3. Timeline for Intervention and Follow-Ups

D.4.2. Mobile Contingency Management for AUD Procedures

As shown in Figure 3, participants will begin one week of practice mCM monitoring at session two of CBT so they can troubleshoot any difficulties they have using the app. The beginning of contingent reinforcement (i.e., the target quit date) is scheduled for the same date as session three of CBT (week 3), which will provide eight weeks of mCM before the end of CBT. Patients who attend all weekly appointments will have two sessions of CBT occurring after mCM ends to assist in preventing relapse when monetary reinforcement is removed.

Table 2. Virtual Scratch-Off Lottery Ticket Reinforcement Amounts				

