Number of Possible Prizes	Size of Prize	Odds per Ticket	Cost per Ticket	Number Expected per Week*
500	\$0	2:1	\$0.00	20
239	\$1	4:1	\$0.24	10
125	\$2	8:1	\$0.25	5
65	\$5	15:1	\$0.33	2.7
40	\$10	25:1	\$0.40	1.6
30	\$20	33:1	\$0.60	1.2
1	\$100	1000:1	\$0.10	<1
Total cost per ticket = \$1.92				
*Expected cost for CM per patient = \$601				
Note *assumes perfect adherence. Participants with perfect adherence can earn up to 34 tickets in week 1 of CM with a maximum of 40 tickets for weeks 2-8 (maximum of 314 tickets over 8 weeks). The intermittent reinforcement schedule follows principles designed by Petry and is designed to ensure that participants can earn at least one “large” (\$20) prize per week for demonstrated abstinence.				

We will reinforce abstinence using an intermittent reinforcement schedule that has demonstrated efficacy and has been widely implemented in VHA (DePhilippis et al., 2018). For each BAC reading that tests negative, the participant will earn virtual scratch-off lottery tickets (scratch-offs) that contain 1000 potential values (see Table 2). Participants will be provided one scratch-off for their first bioverified negative BAC reading, and the number of scratch-offs will increase by one, up to a maximum of four, for each consecutive bioverified negative BAC reading. The number of tickets will be reset to one for any positive (BAC > 0.02) or missed BAC reading. This reinforcement structure is designed to result in an average of \$1.91 of reinforcement per ticket. Adding in the average of \$11 for the practice week, there is an expected total possible of \$611 in abstinent-contingent reinforcement.

Based on procedures used in our mCM for AUD pilot study, participants will be prompted an average of ten times weekly during waking hours to provide video bioverification of BAC within the next 60 minutes. Though prompts are programmed to occur at unpredictable intervals throughout the day, prompts will be scheduled to occur on at least five identified high-risk time periods per week, which are typically the five hours preceding bedtime. At least one prompt will be scheduled for the first two hours of scheduled waking to assess the previous night's drinking.

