D.8.1. Diagnostic Assessment and Psychiatric Symptom Measures. We will assess AUD and other major psychiatric disorders with the Structured Clinical Interview for DSM-5 (SCID-5). Our group has trained diagnostic interviewers for our studies using training videos, observation of live interviews, and monthly meetings to prevent rater drift. Inter-rater reliability across previous interviewers has been excellent (kappa = .96). We will administer the Clinical Institute Withdrawal Assessment to assess past alcohol withdrawal symptoms. Due to the high comorbidity with AUD, we will measure severity of PTSD symptoms with the PTSD Checklist-5 and measure depressive symptoms with the Patient Health Questionnaire-9. At each session, participants will be asked four questions regarding suicidality. The items will be used to examine how the co-occurring mental health problem of suicidal thoughts and behaviors impacts the progression of AUD treatment, as well as the extent to which this treatment simultaneously reduces alcohol use and the occurrence of suicide-related phenomena.

D.8.2. Alcohol-related Measures. Standard self-report and interview-based alcohol-related assessment measures (e.g., severity, craving, consequences; see Table 2) will be used to measure alcohol-related behaviors, perceptions, and attitudes. The Alcohol Purchase Task will be used to provide a behavioral economic measure of the relative reinforcing efficacy of alcohol (Kiselica, Webber, & Bornovalova, 2016).

D.8.3. Self-Efficacy Measures. Attitudes toward behavior change with respect to alcohol will be measured with Alcohol Abstinence Self-Efficacy scale which has demonstrated reliability and validity. Additionally, the Alcohol Readiness to Change will assess motivation to quit alcohol.

Table 3. Measures Administered at Major Study Time Points

Measure	Completer	Time				
		Screen	Txt Session	Post-txt	6-mo. f/u	12-mo. f/u
Diagnostic Assessment						
SCID-5	Study staff	X				
Clinical Institute Withdrawal Assessment	Study staff	X				
Psychiatric Symptom Measures						
PTSD Checklist-5	Participant	X		X	X	X
Patient Health Questionnaire	Participant	X		X	X	X
Suicidality Questions	Study staff	X	X	X	X	X
Alcohol-Related Measures						
AUDIT	Participant	X		X	X	X
BAM	Participant	X		X	X	X
BAM -C	Participant		X			
Penn Craving	Participant	X		X	X	X
Drinker Inventory of Consequences	Participant	X		X	X	X
Alcohol Abstinence Self-Efficacy	Participant	X		X	X	X
NIAAA Alcohol Use Frequency	Participant	X				

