E.1.1. Potential Risks. With regards to completing study measures, there is a risk of discomfort or distress in answering questions. However, distress and discomfort related to questionnaire completion and the psychiatric interview are usually temporary and well-tolerated. Participants are informed that they may refuse to answer any questions while completing the questionnaires. Risks also include discomfort related to alcohol withdrawal. Symptoms of alcohol withdrawal may include headache, insomnia, sweating, shakiness, and rarely, seizures or hallucinations. We will minimize risk of alcohol withdrawal by screening participants at high risk for withdrawal out of the study. However, in case enrolled patients experience alcohol withdrawal that is not reported at the screening visit, we will instruct patients to report symptoms to research staff. There are risks related to participants providing a blood fingerstick. The risks of having a blood puncture includes temporary pain for the needle stick, bruising, and rarely, infection. Some people may experience dizziness, possibly lightheadedness, or rarely, fainting. Finally, there is a potential risk associated with the loss of confidentiality of study data. Because of these risks, the data and safety monitoring plan (DSMP) for this trial focuses on monitoring by the principal investigator (PI), the study physician, and the study coordinator, along with prompt reporting of unexpected and serious adverse events to NIH and to the Institutional Review Board at DUMC.

E.1.2. Potential Benefits. While participants may benefit from quitting or reducing alcohol use, there are no guaranteed benefits to the individual participant and no immediate benefits of the proposed research to others. There are potential benefits to others from the information generated that potentially will be helpful in developing more effective treatment interventions for veterans with AUD.

E.1.3. Protections Against Risk. The study is completely voluntary and participants are informed that they are free to refuse to answer any items on the questionnaires or questions from the interview that they do not wish to answer. They are also informed that they are free to decline participation in any procedure and can withdraw from the study at any time.

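### Alcohol withdrawal is a named study risk, yet nothing scheduled asks about it after screening; one scripted question at existing visits would capture it more completely

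*Combined protocol and SAP*

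**What the plan says.** Section E.1.1 counts withdrawal among the study risks, with seizures and hallucinations as rare forms. It plans to lower that risk by screening out people likely to have it. For the remainder, in case "enrolled patients experience alcohol withdrawal that is not reported at the screening visit, we will instruct patients to report symptoms to research staff". Section E.2 repeats the instruction to report promptly, and withdrawal is the only negative effect of treatment that it names.

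The instrument is described in section D.8.1: "We will administer the Clinical Institute Withdrawal Assessment to assess past alcohol withdrawal symptoms". Table 3 marks it at screening and at no later time. The same section shows a different approach to another safety topic: "At each session, participants will be asked four questions regarding suicidality". Table 3 assigns those questions to study staff at screening, treatment sessions, post-treatment and both follow-ups.

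On timing, section D.3 says "Participants who screen in will be randomized at the first treatment session". Section D.4.2 sets the quit date: "The beginning of contingent reinforcement (i.e., the target quit date) is scheduled for the same date as session three of CBT (week 3". That date is defined through the start of mCM reinforcement, and no separate date is given for CBT alone.

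Section D.2 excludes people who "have fewer than 3 days of abstinence" or who "have a history of clinically significant alcohol withdrawal, as indicated by" a CIWA score of 10 or more, past medical detoxification, or seizures or hallucinations in withdrawal. Any seizure in adult life is also an exclusion.

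**The concern.** The plan commits to monitoring withdrawal but schedules no way of asking about it once treatment starts. The one structured look comes before randomisation and concerns past symptoms, whereas participants are asked to stop or cut down later. An event then becomes known only if the participant mentions it or staff happen to notice it. The medical monitor reviews reports that the study coordinator sends, so an event nobody mentions does not reach that person.

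What is at stake is the completeness of safety information and the chance to escalate a case. The efficacy results are not affected.

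**Working it through.** The documents give no withdrawal rate and no figure to reproduce on this point, so the check compares the schedule with the text and then counts the workload of the fix.

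**1. Scheduled withdrawal assessments after screening.** Table 3 has one withdrawal instrument, the CIWA, marked at screening only. Treatment sessions, post-treatment, 6 months and 12 months have none: 0 after screening.

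**2. Other safeguards, taken one by one.**
- Medical clearance and the medical monitor's review of reported events (E.2): the first acts at entry, the second depends on a report being made.
- Staff contact, a telephone line, weekly meetings and real-time event monitoring (E.2): no withdrawal question and no set time.
- The statement on watching symptom levels closely (E.1.3, Protections Against Risk): no symptom, instrument or schedule.
- Drinking reports at each session (D.8, D.8.8): consumption, not withdrawal.
- BAM-C at each session (Table 3): its items are not shown, so it cannot be judged either way.
- Insomnia Severity Index at post-treatment (Table 3): insomnia is one of the symptoms listed in E.1.1, but the scale is not presented as a withdrawal measure.
- VA records and self-reported non-VA care (D.6, D.8.9): these could show withdrawal serious enough to need care, but they serve the cost and utilisation analyses and are not real-time monitoring.

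**3. Timing.** Session 1 to session 3 is 2 weekly intervals: 2 × 7 = 14 days. The interval from screening to session 1 is not stated and comes on top.

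**4. Contacts with the added question.** 12 CBT sessions + 1 post-treatment visit = 13 per participant. Those covering time after session 1: 11 + 1 = 12. Those covering time after session 3: (12 − 3) + 1 = 10.

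**5. Number of questions and staff time.**
- Full attendance: 140 × 13 = 1,820.
- Lower scenario, using the 119 treatment completers in section F and assuming that the other 21 leave after session 1: 140 + 119 × 12 = 1,568.
- At an assumed 1 to 2 minutes each: 1,568 × 1 / 60 = 26.1 hours to 1,820 × 2 / 60 = 60.7 hours over the whole trial.

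**6. CIWAs triggered (positive rates assumed).**
- 5% to 20% of participants positive once: 140 × 0.05 = 7 to 140 × 0.20 = 28.
- 5% to 20% of contacts positive: 1,568 × 0.05 = 78.4 to 1,820 × 0.20 = 364.

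The second range is plausible because headache and insomnia, both listed in E.1.1, are not specific to withdrawal, and D.8.1 notes high PTSD and depression comorbidity.

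**7. Attendance by arm.** Hypothesis 1a expects better engagement with CM. If participants attended 8 sessions under CBT alone and 10 under CM (assumed), plus post-treatment, they would answer 9 and 11 questions: 11 / 9 = 1.22. At 6 and 10 sessions: 11 / 7 = 1.57.

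**The case against.** The best defence is that entry screening has already removed most of the risk, that participants see staff weekly, and that a medical monitor is in place. That stands as far as it goes: the residual risk is low, and nothing in the documents shows that an event would be missed. But E.1.1 itself provides for withdrawal in enrolled patients, and the provision it makes is passive.

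Two stronger readings are tempting, and the documents support neither.

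First, a reader might infer that the current plan biases a comparison of withdrawal between arms, because under mCM "participants will be prompted an average of ten times weekly during waking hours". That is 10 × 8 = 80 prompts per participant, or 90 with the practice week, against none in CBT alone. But the prompts request a breath-alcohol video, and D.4.2 describes the staff notes as feedback on scratch-off rewards. Nothing presents the app as a route for reporting symptoms. Section F plans no comparison of withdrawal by arm. One can construct a doubling, for instance 70 × 0.10 × 0.30 = 2.1 reports against 70 × 0.10 × 0.60 = 4.2, but the ratio is just the assumed 60% reporting divided by the assumed 30%. Unequal capture is possible and remains speculative.

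Second, a reader might infer that a scripted question would capture withdrawal equally in both arms. The wording and schedule would be equal, but the number of answers need not be, since CM is expected to raise attendance. Asking about the time since the last visit narrows the difference only for participants who come back.

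**Conclusion.** The point holds as a modest safety improvement. Withdrawal has 0 scheduled assessments after screening, and its later capture rests on participants volunteering symptoms, with general channels behind that. A scripted question would bring the scheduled number to 13 per participant in each arm.

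The benefit is more complete capture and escalation. It cannot be sized from the documents, and it would not speed the detection of acute symptoms between visits. The workload figures rest on assumed minutes per question, assumed positive rates and the attendance scenarios above. The case does not depend on any claim of bias between arms. BAM-C is the main uncertainty: if its items cover withdrawal, the gap is smaller.

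**What to change.** In Table 3, add one scripted withdrawal question, asked by staff and covering the time since the last visit, with the same wording and schedule in both arms. Place it beside the suicidality questions at each CBT session and at post-treatment, and ask it at post-treatment of those who stopped treatment early as well. Asking it before randomisation at session 1 makes that answer a baseline. After a positive answer, give the CIWA and notify the medical monitor; the clinical response to a given score is for the sponsor to set. Keep the instruction to report symptoms as soon as possible, because a weekly question looks backward.

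The cost is a protocol amendment and a minute or two at each of 13 existing contacts. The fix needs no new visits, staff or instruments. The downsides are more recorded mild or non-specific events and a number of CIWAs that cannot be fixed in advance, so the positive rate should be watched early on.
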